Appendix 1. Empirical Estimation of Relative Event Rate

Traditionally, Poisson distribution has been assumed to draw inference for the rate of rare events. When the event is rare and the sample size is large, it is known that the overall number of events is approximately from Poisson distribution. However, for the insulin naïve population, the patient-reported hypoglycemia data could be sparse, so that the total number of events may not be distributed from Poisson and may be over-dispersed. Assuming Poisson distribution may significantly underestimate the variance, and therefore may reduce the coverage probability and inflate the Type-I error. An empirical method in estimating the variance of the relative event rate without assuming any distribution on the number of events will be provided in this appendix.

Let X_{ij} denote the count response variable for patient j in treatment group i . Let $Y_i = \sum_j X_{ij}$ be the total number of events for treatment group i , and T_i denote the exposure for treatment group i . Let $i = 0$ for the control group and $i = 1$ for the experimental treatment group. The event rate for treatment group i can be calculated as

$$\hat{r}_i = \frac{Y_i}{T_i}$$

The empirical variance of \hat{r}_i is

$$\widehat{Var}(\hat{r}_i) = T_i^{-2} \widehat{Var}(Y_i) = T_i^{-2} n_i S_i^2,$$

where S_i^2 is the variance of X_{ij} for treatment group i . Using the delta-method, the variance of $\log(\hat{r}_i)$ can be estimated as

$$\widehat{Var}(\log(\hat{r}_i)) = Y_i^{-2} n_i S_i^2$$

The relative rate of the experimental treatment versus the control treatment is estimated as

$$\hat{\lambda} = \frac{\hat{r}_1}{\hat{r}_0}$$

The variances of $\hat{\lambda}$ and $\log(\hat{\lambda})$ are

$$\widehat{Var}(\hat{\lambda}) = \hat{\lambda}^2 \widehat{Var}(\log(\hat{\lambda}))$$

$$\widehat{Var}(\log(\hat{\lambda})) = \widehat{Var}(\log(\hat{r}_0)) + \widehat{Var}(\log(\hat{r}_1)) = Y_0^{-2} n_0 S_0^2 + Y_1^{-2} n_1 S_1^2$$

Assuming $\log(\hat{\lambda})$ is asymptotically from a normal distribution, the $100(1 - \alpha)\%$ confidence interval for $\log(\hat{\lambda})$ can be constructed as

$$\left[\log(\hat{\lambda}) - z_{1-\frac{\alpha}{2}} \sqrt{\widehat{Var}(\log(\hat{\lambda}))}, \log(\hat{\lambda}) + z_{1-\frac{\alpha}{2}} \sqrt{\widehat{Var}(\log(\hat{\lambda}))} \right]$$

Then, the $100(1 - \alpha)\%$ confidence interval for $\hat{\lambda}$ is

$$\left[\hat{\lambda} \exp\left(-z_{1-\frac{\alpha}{2}}\sqrt{\widehat{Var}(\log(\hat{\lambda}))}\right), \quad \hat{\lambda} \exp\left(z_{1-\frac{\alpha}{2}}\sqrt{\widehat{Var}(\log(\hat{\lambda}))}\right) \right] \quad (1)$$

The p-value for testing the null hypothesis of $H_0: \lambda = 1$ is calculated as

$$p = 2\Phi\left(|\log(\hat{\lambda})|/\sqrt{\widehat{Var}(\log(\hat{\lambda}))}\right) \quad (2)$$

Leo Document ID = 53a27c89-8b4a-4ce2-8c1a-837051850933

Approver: PPD

Approval Date & Time: 08-Sep-2021 12:28:27 GMT

Signature meaning: Approved

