4.2.2. Safety

To investigate the safety of LY3209590 compared with insulin degludec for the following endpoints:

1. Incidence and rate of hypoglycemia events during the treatment period;
2. Incidence of treatment-emergent serious adverse events (TE-SAEs).

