4.3. Exploratory Objectives

To investigate other safety and efficacy measures for LY3209590 for the following endpoints:

1. Insulin dose at baseline and Week 26;
2. Treatment-emergent adverse events (TEAEs);
3. Incidence and rate of hypoglycemia events during the post-treatment follow-up period;
4. Discontinuation of investigational product (IP) due to adverse events (AEs);
5. Clinical laboratory results;
6. Injection site reactions;
7. Liver aminotransferase change from baseline to Weeks 12 and 26;
8. Triglyceride and FFA change from baseline to Weeks 12 and 26;
9. Body weight change from baseline at Weeks 12 and 26;
10. Glucose time in target range, time in hyperglycemia, time in hypoglycemia using FGM
11. Lipids (cholesterol, LDL, HDL, triglycerides);
12. Six-point self-monitoring of blood glucose (SMBG) profiles;

13. The frequency of antibody formation to LY3209590;
14. Incidence and percentage of missed doses of LY3209590 and insulin degludec.

5. A Priori Statistical Methods

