the observed data with collection date before or on the last dose date +10 days). Sensitivity analyses for selected efficacy measures may be conducted on the Randomized Population using the data up to the study treatment discontinuation.

Unless otherwise stated, the safety analyses will be conducted on the safety analyses set based on the Safety Population using all data collected during the study including treatment and follow-up periods regardless of the treatment disposition status. The safety measures will be summarized and compared between LY3209590 (by pooling LY3209590 Algorithm 1 and LY3209590 Algorithm 2 data) and insulin degludec. Safety parameters derived from FGM measures will be summarized and compared between LY3209590 Algorithm 1 and insulin degludec.

Unless otherwise specified, the baseline value used for the analyses will be the last non-missing value obtained for each participant prior to or on the date of first study IP dose (or randomization visit date if first dose date is missing). The baseline liver enzyme lab measures will be the average of all assessments prior to and at randomization visit.

All tests of treatment effects will be conducted at a 2-sided alpha level of 0.1, unless otherwise stated, and all confidence intervals (CIs) will be given at a 2-sided 90% level.

Puerto Rico and the United States (US) are always pooled in the analysis, as Puerto Rico will be considered part of US during randomization. All analyses using country in the model will use pooled country, unless otherwise specified. No other pooling of countries is needed.

For continuous measurements, summary statistics will include sample size, mean, median, standard deviation (SD), minimum, and maximum. For certain variables that are considered to be log-normally distributed, the geometric mean and coefficient of variation (CV) will be provided instead.

For categorical measurements, summary statistics will include sample size, frequency, and percentage. Fisher's exact test will be used. Chi-squared test will be used for multi-category variables.

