5.10.3.2. Hypoglycemia Events

According to the 2020 American Diabetes Association standard of medical care in diabetes, there are two levels of hypoglycemia defined by glucose concentration:

- Level 1: glucose <70 mg/dL (3.9 mmol/L) and glucose \geq 54 mg/dL (3.0 mmol/L)
- Level 2: glucose <54 mg/dL (3.0 mmol/L)

With the above glucose reading requirement for Level 1 and 2 hypoglycemia, the following type of hypoglycemia events will be derived: documented hypoglycemia, documented nocturnal hypoglycemia (occurs between bedtime and waking), and documented non-nocturnal hypoglycemia (occurs between waking and bedtime).

Per the study protocol, severe hypoglycemia is reported as a serious AE. Severe hypoglycemia is defined in the protocol and is consistent with the ADA definition, but also requires investigator confirmation of neurological impairment. The 2020 American Diabetes Association standard of medical care in diabetes also classified severe hypoglycemia as Level 3 hypoglycemia. During a severe hypoglycemia episode, the participant has an altered mental status and cannot assist in his/her own care, may be semiconscious or unconscious, or experience coma with or without seizures, and may require assistance of another person to actively administer carbohydrate, glucagon, or other resuscitative actions. This information will be collected in the patient eDiary and the severe hypoglycemia will be listed.

[Table BDCL.1](#) provides the summary of statistical method for hypoglycemia event related analysis. Additionally, severe hypoglycemia events will be listed. The severe hypoglycemia reported as spontaneous AE in the eCRF will also be summarized by MedDRA PT. The Level 2 and Level 3 are usually considered as clinically significant hypoglycemia. Therefore, the analysis on a composite of Level 2 and Level 3 (denoted as Level 2/3) hypoglycemia will also be conducted.

Table BDCL.1. Hypoglycemia Event Related Analyses

Endpoint	Time Point*	Statistical Method
Rate of hypoglycemia events for Level 1 and Level 2/3 
 • Documented • Nocturnal • Non-Nocturnal 	0-12, 0-26, 12-26 weeks, post-treatment period (up to Visit 801)*	Exposure-adjusted rate per year / 100 years (calculated by total number of events divided by total exposure for individual patients) will be provided and the empirical method (see Appendix 1 for details) will be used for treatment comparison.

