5.11.2. FGM Variable and Analysis

The continuous variables derived from FGM will be summarized and compared between treatment groups by visit using MMRM model. The model will include the treatment, HbA1c stratum (<8.5% or ≥8.5%), baseline value of the dependent variable, visit, and treatment by visit interaction. The raw mean and LS mean difference between treatment groups will be summarized.

For the between-day and within-day glucose variability, the variable will take log-transformation before performing the MMRM analysis.

The binary variables will be analyzed using a longitudinal logistic regression. In the longitudinal logistic regression model, the independent variables of treatment, baseline HbA1c value, baseline continuous variable corresponding to the binary dependent variable, visit, and treatment by visit interaction will be used.

For the hypoglycemia episodes defined by FGM, the analysis using a negative binomial model with the offset of log (exposure in year) will be performed. The model will include treatment and baseline HbA1c.

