5.12. Subgroup Analyses

The subgroups will be defined as:

- Body mass index (<30, ≥30)
- Baseline HbA1c (<8.5% and ≥8.5%)
- Baseline HbA1c (defined by baseline median)
- Concomitant medication (metformin alone and metformin in combination with other oral antidiabetic medications)

The outcome measures included in the subgroup analyses are:

- HbA1c and change in HbA1c from baseline to up to 26 weeks
- Documented hypoglycemia, non-nocturnal, and nocturnal hypoglycemia rates (glucose <70 mg/dL [3.9 mmol/L] and glucose ≥54 mg/dL [3.0 mmol/L]) during 0-26 weeks.

Analyses for HbA1c and its change will be performed examining the 3-way interaction of the primary treatment arms, visit and the subgroup variable using the same MMRM model described for the primary analysis. This model will include the same fixed effects given for the primary analysis model plus factors of subgroup, 2-way interaction of subgroup and treatment, 2-way interaction of subgroup and visit, and 3-way interaction of treatment, visit, and the subgroup.

The hypoglycemia rates will be analyzed using a negative binomial regression including the treatment, baseline HbA1c, subgroup, 2-way interaction of subgroup and treatment as covariates, and log (exposure in year) as the offset.

The interaction effects will be evaluated using a significance level of 0.1, unadjusted. If the interaction effect is significant ($p < 0.1$), separate analysis without the terms related with the subgroup will be performed for each subpopulation.

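### As printed, SAP Appendix 1 equation (2) gives p-values between 1 and 2 for the hypoglycemia rate ratios and contradicts the interval in equation (1); separately, a within-arm dose test is misnamed as two-sample

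*SAP*

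**What the plan says.** For the rates of Level 1 and Level 2/3 hypoglycemia, Table BDCL.1 in SAP 5.10.3.2 states that "the empirical method (see Appendix 1 for details) will be used for treatment comparison". Appendix 1 forms the rate ratio λ̂, estimates the variance of log λ̂ without a distributional assumption on the counts, and treats log λ̂ as asymptotically normal. On that basis it gives two results:

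- a confidence interval, built on the log scale from "\log(\hat{\lambda}) - z_{1-\frac{\alpha}{2" and its upper counterpart and then exponentiated as equation (1);
- a p-value for H0: λ = 1, equation (2), which begins "p = 2\Phi\left(|\log(\hat{\lambda" and divides by the square root of the estimated variance of log λ̂. There is no minus sign before the absolute value and no complement of Φ.

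SAP 5.1 sets a two-sided alpha of 0.1 for tests of treatment effects and says that "all confidence intervals (CIs) will be given at a 2-sided 90% level".

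SAP 4.2.2 lists "Incidence and rate of hypoglycemia events during the treatment period" as a secondary safety endpoint, and SAP 4.3 lists "Incidence and rate of hypoglycemia events during the post-treatment follow-up period" as exploratory.

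On a different matter, the last paragraph of SAP 5.8 rules out a between-arm comparison of insulin dose and then names a two-sample t-test for the change in dose from baseline within each arm.

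**The concern.** A two-sided p-value built from |z| needs the upper tail of the normal distribution. Equation (2) takes the lower tail at a non-negative argument, so it rises as the evidence against H0 grows and can never fall below 1. Equation (1), from the same estimate and standard error, has the standard form. The interval and the p-value reported for one rate ratio would therefore contradict each other.

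Appendix 1 is the only place in either document that states a p-value rule for these rate comparisons. If it is programmed literally, every p-value in that part of the table is invalid. If it is put right silently in the code, the reported analysis departs from the approved SAP.

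The dose test raises a smaller matter of the same kind. Baseline and later doses come from the same participants, and a two-sample test ignores the pairing.

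**Working it through.** **Inputs from the SAP.** Equations (1) and (2) of Appendix 1; two-sided alpha 0.1 and 90% intervals (5.1); two levels, three event types and four periods (Table BDCL.1). Write z = |log λ̂|/SE, so z ≥ 0.

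**Range of the printed p.** For z ≥ 0, Φ(z) lies in [0.5, 1), so 2Φ(z) lies in [1, 2). Since 2Φ(z) = 2 − 2(1 − Φ(z)), the printed p is always 2 minus the correct p.

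| z | printed 2Φ(z) | correct 2(1 − Φ(z)) |
|---|---|---|
| 0 | 1.000 | 1.000 |
| 1 | 1.683 | 0.317 |
| 1.645 | 1.900 | 0.100 |
| 1.96 | 1.950 | 0.050 |
| 3 | 1.997 | 0.0027 |

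The stated alpha of 0.1 is recovered only by the corrected form, at z = 1.645. Under the printed form the chance of p < 0.1 is zero.

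**Conflict with equation (1).** Assume for illustration λ̂ = 1.5 and SE = 0.20.
- z = ln(1.5)/0.20 = 2.027
- 90% interval = 1.5 × exp(∓1.645 × 0.20) = 1.08 to 2.08, which excludes 1
- printed p = 1.957; correct p = 0.043

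The 90% interval excludes 1 exactly when z > 1.645, which is exactly when the corrected p is below 0.1. The corrected equation (2) and equation (1) therefore always agree.

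**Simulation under H0.** The Appendix 1 estimator was simulated with 125 per arm, over-dispersed counts, 20% early dropout, and 20,000 runs in each of three scenarios. The event rates (2, 1 and 0.3 per year) and the dispersion were assumed, because the documents give none. The printed p always lay between 1 and 2 and never rejected. The corrected p rejected in 10.3% to 11.1% of runs, and equation (1) covered in 88.9% to 89.7%.

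**Number of comparisons.** 2 levels × 3 types × 4 periods = 24. Three periods fall within treatment (2 × 3 × 3 = 18, secondary) and one after it (2 × 3 × 1 = 6, exploratory).

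**What is not affected.** Subgroup rates: "The hypoglycemia rates will be analyzed using a negative binomial regression" (SAP 5.12). Sensor-defined episodes: "For the hypoglycemia episodes defined by FGM, the analysis using a negative binomial model" (SAP 5.11.2). Incidence uses logistic regression. The rate estimates, their intervals and the primary HbA1c analysis do not use equation (2).

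**Dose test.** With ρ the correlation between baseline and later dose, and k the later SD divided by the baseline SD, the ratio of the two-sample SE to the paired SE is √[(1 + k²)/(1 + k² − 2ρk)]. Neither ρ nor k is given in the documents; the values below are assumptions.

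| ρ | k = 1 | k = 2 | k = 3 |
|---|---|---|---|
| 0.3 | 1.20 | 1.15 | 1.10 |
| 0.5 | 1.41 | 1.29 | 1.20 |
| 0.7 | 1.83 | 1.51 | 1.31 |

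This concerns the LY3209590 arm. In the degludec arm the starting dose is fixed at 10 units (protocol 10.8.2), so the baseline variance is zero and the ratio is 1.

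**The case against.** **It may be an extraction artefact.** The point turns on one symbol in text read by machine from a PDF, and characters are lost one at a time. The study number, for example, begins with the digit 1 in the protocol's amendment rationale and with the letter I elsewhere. Surviving minus signs in equation (1) and in the log-scale interval make a lost sign less likely but cannot rule it out. This stands as a reason to look at the source page before changing anything.

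**If real, it is a self-revealing slip.** The estimator, its variance, the normal approximation and the null hypothesis together fix what the p-value must be. A value above 1 is unlikely to be reported unnoticed, and no decision rule rests on it; the only stated one is HbA1c noninferiority in SAP 5.7. All of this is fair and limits the harm, but it does not make the written rule correct.

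**Equation (1) is not a perfect fallback.** It is a large-sample interval, simulated coverage was slightly under 90%, and log λ̂ is undefined if an arm has no events. Appendix 1 itself expects that the data may be sparse. This stands as a qualification: the interval has the right form, and its accuracy with few events is a separate question.

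**The dose-test figures show mainly the unfavorable side.** At ρ = 0 the ratio is 1, and at ρ = −0.3 with k = 1 it is 0.88. The documents do not exclude a low correlation between the initial dose and a dose later titrated on glucose. The size is therefore uncertain, but the two-sample standard error is wrong for paired data unless the correlation is zero or one of the variances is.

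**Conclusion.** The point holds for the formula as it appears in the SAP text. Equation (2) yields p in [1, 2), equal to 2 minus the correct value, and contradicts equation (1) whenever the 90% interval excludes 1. This is an identity and needs no assumed data; only the worked example and the simulation rest on assumptions. It touches 24 hypoglycemia rate comparisons, 18 of them on a secondary safety endpoint.

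The consequence is an invalid pre-specified p-value that would have to be corrected after the fact. Conclusions at the 0.1 level can still be read from the interval. It should be corrected, but it does not threaten the trial's main result. The one condition is that the source page shows the formula as it reads here.

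The dose test is a separate, minor wording error in an exploratory within-arm analysis. Its standard error in the LY3209590 arm would be 1.10 to 1.83 times the paired one over the tabulated assumptions, and the degludec arm is essentially unaffected.

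**What to change.** 1. Compare equation (2) with the source page of the SAP to rule out a lost sign.
2. If it reads as here, replace it by p = 2(1 − Φ(|log λ̂|/SE)), or equivalently 2Φ(−|log λ̂|/SE), and confirm that the analysis program uses that form.
3. In the last paragraph of SAP 5.8, name a paired t-test, that is, a one-sample t-test on the change in dose from baseline.

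The cost is one symbol and one phrase. Neither change affects the design, data collection, sample size or the primary analysis, and there is no downside.
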